8.3.2 Dose Adjustments

In General

Dose adjustments are to be made according to the system showing the greatest degree of toxicity. Once dose is reduced due to adverse events, patients should not be re-challenged to a higher dose level.

Dose reductions or delays will be considered for the standard endocrine treatment and ribociclib and may occur independently.

Due to the wide spectrum of feasible combinations of standard endocrine treatment and ribociclib dose reductions and delays of standard endocrine treatment should follow general GCP criteria for the application of antineoplastic drugs (Repetto et al. 2003, NCCN-Guidelines) and should be made according to the SPC and/or investigator's brochure. The latest versions of the SPCs ("Fachinformation" according to German Drug Law) of the standard therapy will be provided on the DETECT IV website or by contact the DETECT Study Office in Ulm (Univeritäts-frauenklinik Ulm, Studienzentrale, [name], [name], [contact], [contact], Email: [contact]).

Subjects who require permanent discontinuation of one of the products due to unacceptable toxicities may switch to another treatment regime of the standard endocrine treatment if medically reasonable.

The antineoplastic treatment of a patient can be postponed for up to 4 weeks to allow resolution of toxicity. The investigator must consult the DETECT IV Study Office prior continuing therapy for any patient requiring a delay of study treatment of more than two weeks for any reason.

All patients who require permanent discontinuation of both ribociclib and the endocrine agent in a given treatment combination will be withdrawn from the treatment intervention schedule (start of the 2-year follow-up period).

8.3.2.1 Permitted study drug dose adjustments and interruptions

For patients who are unable to tolerate the protocol-specified dosing scheme, dose adjustments and interruptions are permitted in order to keep the patient on the study drugs. The following guidelines should be followed.

These changes must be recorded on the Dosage Administration Record eCRF.

Treatment with ribociclib and standard endocrine therapy should continue as long as clinical benefit is observed or until unacceptable toxicity occurs. Management of severe and/or intolerable suspected adverse events may require temporary dose reduction and/or interruption.

For patients who do not tolerate the protocol-specified ribociclib dosing schedule, dose adjustments are permitted in order to allow the patient to continue the study. The following guidelines need to be applied:

All study drug interruptions or dose modifications must be recorded on the Dosage Administration Record page of the eCRF.

	Dose	Number of tablets & strength
Starting dose	600 mg/d	3 x 200 mg tablets
First Dose reduction	400 mg/d	2 x 200 mg tablets
Second dose reduction	200 mg/d	1 x 200 mg tablets

Table 19: Ribociclib Dose Modification guidelines

If a patient has already decreased ribociclib intake to 200 mg every other day, no further dose reduction is permitted. Patients requiring an additional ribociclib dose reduction will be required to discontinue study treatment.

Patients who interrupt ribociclib therapy for more than 4 weeks must be discontinued from the study.

TABLE 20, TABLE 21, TABLE 22 and TABLE 23 provide the procedure to be followed for ribociclib dose modification in the event of toxicities suspected to be related to the ribociclib treatment. Included are also instructions for re-initiation of ribociclib dosing once sufficient recovery of toxicity is seen.

Toxicity	Actions
HEPATOTOXICITY (BILIRUBIN; SGPT/ALT, SGOT/AST)	
TOTAL BILIRUBIN without ALT/AST increase above base-line value	
Grade 1 (> ULN-2.0 x ULN) : Maintain dose level with LFTs monitored bi-weekly
 
Grade 2 (> 2.0 ULN - 3.0 x ULN): Dose interruption of ribociclib If resolved to ≤ grade 1 in ≤ 21 days, then maintain dose level If resolved to ≤ grade 1 in > 21 day or toxicity recurs, then reduce 1 dose level Repeat liver enzymes and bilirubin tests twice weekly for two weeks after dose resumption If toxicity recurs after two dose reductions, discontinue ribociclib
 
Grade 3 (> 3.0 ULN -10.0 x ULN):: Dose interruption of ribociclib If resolved to ≤ grade 1 in ≤ 21 days, lower 1 dose level of ribociclib Repeat liver enzymes and bilirubin tests twice weekly for two weeks after dose resumption
 
If resolved to ≤ grade 1 in > 21 days or toxicity recurs, discontinue ribociclib treatment
 
Grade 4 (> 10.0 ULN): Discontinue ribociclib treatment

Confounding factors and/or alternative causes for increase of total bilirubin should be excluded before dose interruption/reduction. They include but are not limited to: evidence of obstruction, such as elevated ALP and GGT typical of gall bladder or bile duct disease, hyperbilirubinemia due to the indirect component (i.e. direct bilirubin component ≤ 1x ULN) due to hemolysis or Gilbert Syndrome, pharmacologic treatment, viral hepatitis, alcoholic or autoimmune hepatitis, other hepatotoxic drugs.
 
For patients with Gilbert Syndrome, these dose modifications apply to change in direct bilirubin only. Bilirubin will be fractionated if elevated.
	
AST or ALT without bilirubin elevation > 2 x ULN	
Same grade as baseline or increase from baseline grade 0 to grade 1 (confirmed 48-72 h later) : No dose adjustment required with LFTs monitored per protocol if same grade as baseline or bi-weekly in case of increase from baseline grade 0 to 1.
 
Increase from baseline 0 or 1 to grade 2 (> 3.0 – 5.0 x ULN): Dose interruption of ribociclib If resolved to ≤ baseline grade in ≤ 21 days or toxicity recurs, then reduce 1 dose level Repeat liver enzyme and bilirubin tests twice weekly for 2 weeks after dose resumption If toxicity recurs after two dose reductions or recovery to ≤ baseline grade is > 28 days, discontinue ribociclib
 
Increase from baseline 0 or 1 to grade 3 (> 5.0 – 20.0 x ULN): Dose interruption of ribociclib until resolved to ≤ baseline until resolved to ≤ baseline grade, then lower 1 dose level of ribociclib Repeat liver enzyme and bilirubin tests twice weekly for two weeks after dose resumption If recovery to ≤ baseline grade > 28 days, discontinue ribociclib If toxicity recurs, discontinue ribociclib
 
Increase from baseline from grade 2 to grade 3 (> 5.0 – 20.0 x ULN): Dose interruption of ribociclib until resolved to ≤ baseline grade, then lower 1 dose level of ribociclib Repeat liver enzyme and bilirubin tests twice weekly for two weeks after dose resumption If toxicity recurs after two dose reductions or recovery to ≤ baseline grade is > 28 days, discontinue
 
Grade 4 (> 20.0 x ULN): Discontinue ribociclib

AST or ALT and concurrent Bilirubin	
For patients with normal ALT and AST and total bilirubin at baseline: AST or ALT > 3.0 ULN combined with total bilirubin > 2 x ULN without evidence of cholestasis OR

For patients with elevated AST or ALT or total bilirubin at baseline: baseline: (AST or ALT > 2 x baseline AND > 3.0 x ULN) OR (AST or ALT 8.0 x ULN) – whichever is lower - -combined with (total bilirubin > 2 x baseline AND \geq 2.0 ULN)

Discontinue ribociclib treatment

Coinfounding factors and /or alternative causes for increased transaminases should be excluded before dose interruption/reduction. They include but are not limited to: concomitant medications, herbal preparations or dietary supplements, infection, hepato-biliary disorder or obstruction, new or progressive liver metastases, and alcohol intake.

Table 20: Ribociclib dose adjustment and management recommendation for hepatic toxicities

Toxicity		
Thrombocytopenia		
 Grade 1 ($\geq 75 \times 10^9$): No change
Platelet count		
 Grade 2 ($50 \times 10^9 - 75 \times 10^9$) Dose interruption until recovery to grade ≤ 1 Reintroduce ribociclib at the same dose level Grade 3 ($25 \times 10^9 - 50 \times 10^9$) Dose interruption until recovery to grade ≤ 1 Reintroduce ribociclib at the same dose level If toxicity recurs at grade 3: temporary dose interruption until recovery to grade ≤ 1 and reduce ribociclib to the next lowest dose level. Grade 4 ($<25 \times 10^9$) Dose interruption until recovery to grade ≤ 1 Reintroduce ribociclib at the next lower dose level. If toxicity recurs at grade 4: discontinue ribociclib.
Absolute Neutrophil count (ANC)	Neutrophil count	
 Grade 1 ($\geq 1,5 \times 10^9$): No change Grade 2 ($1,5 \times 10^9 - 10^9$): No change Grade 3 ($0,5 \times 10^9 - 1 \times 10^9$): Dose interruption until recovery to $\geq 1.0 \times 10^9/L$ Reintroduce ribociclib at the same dose level. If toxicity recurs at grade 3: temporary dose interruption until recovery to $\geq 1.0 \times 10^9/L$ If resolved in ≤ 7 days, then maintain dose level. If resolved in > 7 days, then reduce ribociclib dose to the next lower dose level. Grade 4 ($<0,5 \times 10^9$): Dose interruption until recovery to $\geq 1.0 \times 10^9/L$ Reintroduce ribociclib at the next lower dose level. If toxicity recurs at grade 4: temporary dose interruption until recovery to $\geq 1.0 \times 10^9/L$ And reduce ribociclib at the next lower dose level.
Febrile neutropenia		
 Grade 3 (ANC $< 1.0 \times 10^9/L$ with a single temperature of $> 38.3^\circ C$ or a sustained temperature of $\geq 38^\circ$ for more than one hour): Dose interruption until improvement of ANC $\geq 1.0 \times 10^9/L$ and no fever. Restart at the next lower dose level. If febrile neutropenia recurs, discontinue ribociclib. Grade 4 (Life-threatening consequences; urgent intervention indicated): Discontinue ribociclib.
Anemia (Hemoglobin)		
 Grade 1 ($\geq 10.0 \times LLN$ g/dl): No change Grade 2 ($\geq 8.0 - < 10 \times LLN$ g/dl): No change Grade 3 ($< 8.0 \times LLN$ g/dl):

Dose interruption until recovery to grade ≤ 2 .

Reintroduce ribociclib at the same dose.

• **Grade 4 (Life-threatening consequences; urgent intervention indicated):**

Discontinue ribociclib

Physicians should always manage patients according to their medical judgment based on the particular clinical circumstances.

Table 21: Ribociclib dose adjustment and management recommendations for hematological adverse reactions

Additional follow up for QTc prolongation

For All Grades

- Check the quality of the ECG and the QT value and repeat if it needed
- Perform analysis of serum electrolytes (K⁺, Ca⁺⁺, Phos, Mg⁺⁺). If outside of the normal range, interrupt ribociclib administration, correct with supplements or appropriate therapy as soon as possible, and repeat electrolytes until documented as normal.
- Review concomitant medication usage for the potential to inhibit CYP3A4 and/or to prolong the QT interval.
- Check compliance with correct dose and administration of ribociclib.
- Consider collecting a time matched PK sample; record date and time of last study drug intake

1*

QTc 450-480 ms

No change

2*

QTc 481-500 ms

Interrupt ribociclib.

Perform a repeat ECG within one hour of the first QTcF of ≥ 481 ms.

If QTcF < 481 ms, restart ribociclib at the same dose. No dose adjustment required for first occurrence.

If QTcF remains ≥ 481 ms, repeat ECG as clinically indicated until the QTcF returns to < 481 ms. restart ribociclib at the same dose. No dose adjustment required for first occurrence.

If QTcF ≥ 481 ms recurs, ribociclib should be reduced by 1 dose level.

Repeat ECGs 7 days and 14 days after dose resumption (then as clinically indicated) for any patients who had therapy interrupted due to QTcF ≥ 481 ms

3

QTc ≥ 501 ms on at least two separate ECGs

Interrupt ribociclib. Transmit ECG immediately and confirm prolongation/abnormalities.

Perform a repeat ECG within one hour of the first QTcF of ≥ 501 ms.

If QTcF remains ≥ 501 ms, consult with a cardiologist (or qualified specialist) and repeat cardiac monitoring as indicated until the QTcF returns to < 481 ms.

If QTcF returns to < 481 ms, ribociclib will be reduced by 1 dose level.

Repeat ECGs 7 days and 14 days after dose resumption (then as clinically indicated) for any patients who had therapy interrupted due to QTcF ≥ 501 ms

If QTcF of ≥ 501 ms recurs, discontinue ribociclib.

4* [QT/QTc ≥ 501 or > 60 ms change from baseline] and [Torsades de pointes or polymorphic ventricular tachycardia, or signs/symptoms of serious arrhythmia]

Discontinue ribociclib.

- Obtain local cardiologist (or qualified specialist) consultation and repeat cardiac monitoring as indicated until the QTcF returns to <481 ms.

*All values refer to the average of triplicate measurements

Table 22: Ribociclib dose adjustment and management recommendation for all other adverse reactions

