8.3.3 Guidance for all other adverse reactions

Consider performing an analysis of serum potassium, calcium, phosphorous, and magnesium for all adverse reactions, if indicated. If electrolyte values are outside of the normal range, interrupt ribociclib administration, correct electrolytes with supplements or appropriate therapy as soon as possible, and repeat electrolyte testing until documented normalization of the electrolytes.

Patients who experience renal impairment (not due to other contributing factors) of grade 2 or higher during the treatment period should discontinue treatment and should be followed for safety assessments.

For all other adverse events please follow recommendations in Table 22.

Grade	Ribociclib dose adjustment and management recommendation
1	No dose adjustment recommended. Initiate appropriate medical therapy and monitor.
2	Dose interruption until recovery to grade ≤ 1 . Initiate appropriate medical therapy and monitor. Re-initiate ribociclib at the same dose. If the same toxicity recurs at grade 2, interrupt ribociclib until recovery to grade ≤ 1 . Re-initiate ribociclib at the next lower dose level.
3	Dose interruption until recovery to grade ≤ 1 . Initiate appropriate medical therapy and monitor. Re-initiate ribociclib at the next lower dose level. If toxicity recurs at grade 2: temporary dose interruption until recovery to grade ≤ 1 and reduce ribociclib dose the next lower dose level. If toxicity recurs at grade 3, discontinue ribociclib.
4	Discontinue ribociclib and treat with appropriate medical therapy.

Table 23: Ribociclib dose adjustment and management recommendation for all other adverse reactions

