8.3.3.1 Management of specific toxicities

Additional follow-up for hepatic toxicities

Increase in transaminases combined with total bilirubin (TBIL) increase may be indicative of drug-induced liver injury (DILI), and should be considered as clinically important events.

The threshold for potential DILI may depend on the patient's baseline AST/ALT and TBIL value; patients meeting any of the following criteria will require further follow-up as outlined below:

- For patients with normal ALT und AST and TBIL value at baseline: AST or ALT $> 3.0 \times$ ULN combined with TBIL $> 2.0 \times$ ULN
- For patients with elevated AST or ALT or TBIL value at baseline: (AST or ALT $> 2 \times$ baseline AND $> 3.0 \times$ ULN) OR (AST or ALT $> 8.0 \times$ ULN), whichever is lower combined with (TBIL $> 2 \times$ baseline AND $> 2.0 \times$ ULN)

Medical review needs to ensure that liver test elevations are not caused by cholestasis, defined as: ALP elevation $> 2.0 \times$ ULN with R value < 2 in patients without bone metastasis, or elevation of ALP liver fraction in patients with bone metastasis.

Note: (The R value is calculated by dividing the ALT by the ALP, using multiples of the ULN for both values. It denotes the relative pattern of ALT and/or ALP elevation is due to cholestatic or hepatocellular liver injury or mixed type injury)

In the absence of cholestasis, these patients should be immediately discontinued from study drug treatment, and repeat LFT testing as soon as possible, preferably within 48 hours from the awareness of the abnormal results. The evaluation should include laboratory tests, detailed history, physical assessment and the possibility of liver metastasis or new liver lesions, obstructions/compressions, etc.

Hepatic toxicity monitoring includes the following LFTs: albumin, ALT, AST, total bilirubin, direct and indirect bilirubin, alkaline phosphatase (fractionated if alkaline phosphatase is grade 2 or higher), creatine kinase, prothrombin time (PT)/INR and GGT. For patients with Gilbert Syndrome: total and direct bilirubin must be monitored, intensified monitoring applies to changes in direct bilirubin only.

Close observation is recommended in case of AST, ALT, and/or bilirubin increase requiring dose interruption, which involves:

1. Repeating liver enzyme and serum bilirubin tests **two or three times weekly**. Frequency of re-testing can decrease to once a week or less if abnormalities stabilize or return to normal values.

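### Table 20 leaves some combined bilirubin and transaminase rises on ribociclib without a row, and the fallback in section 8.3.3 names the QTc table

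*Protocol*

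**What the plan says.** Section 8.3.2.1 says its guidelines have to be applied, and section 13.1.1 makes Tables 19 to 23 the interruption and modification rules for the ribociclib cohort. The liver rules are in Table 20:

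- Row 1 is headed "TOTAL BILIRUBIN without ALT/AST increase above base-line value" and gives actions by bilirubin grade, up to grade 4 (above 10 x ULN).
- Row 2 is headed "AST or ALT without bilirubin elevation > 2 x ULN" and gives actions by transaminase grade.
- Row 3 covers concurrent rises and has one action, discontinuation. For normal baseline values the condition is "AST or ALT > 3.0 ULN combined with total bilirubin > 2 x ULN without evidence of cholestasis". For elevated baseline it begins "For patients with elevated AST or ALT or total bilirubin at baseline: baseline: (AST or ALT > 2 x baseline AND > 3.0 x ULN", has an alternative limit at 8.0 x ULN, and adds bilirubin above 2 x baseline and at least 2.0 x ULN. This second limb does not mention cholestasis.

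Section 8.3.3.1 repeats essentially the same combined thresholds for possible drug-induced liver injury, asks for a medical review for cholestasis, and then states: "In the absence of cholestasis, these patients should be immediately discontinued from study drug treatment".

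Section 8.3.3, on all other adverse reactions, says: "For all other adverse events please follow recommendations in Table 22". The table numbered 22 starts with "Additional follow up for QTc prolongation" and contains only QTc management. The generic grade 1 to 4 rules are in Table 23, printed below that sentence. Tables 22 and 23 carry the same caption.

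**The concern.** A set of dose-modification rows should give each laboratory pattern one route. Here each row heading excludes part of the combined pattern and the rows do not meet. A patient with isolated raised bilirubin has an instruction in row 1. If her ALT then also rises, but not above 3 x ULN, row 1 ceases to apply and neither other row begins. A worse laboratory picture thus removes the specific instruction.

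The patterns are open to this population. Section 5.1 admits patients with ALT/AST up to 3.0 x ULN and bilirubin up to 2.0 x ULN, and liver metastases are exempt from the liver exclusion. Section 8.3.3.1 itself describes combined rises as clinically important. With up to 100 centers, each site would have to choose its own route through binding rules. Ribociclib exposure, interruptions and discontinuations could then partly reflect how the table was read.

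**Working it through.** The protocol gives no figure to reproduce. The check applies the three row conditions literally to example values, all in multiples of ULN.

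| Baseline ALT / bilirubin | On treatment ALT / bilirubin | Cholestasis | Row 1 | Row 2 | Row 3 |
|---|---|---|---|---|---|
| 0.8 / 0.8 | 0.8 / 3.5 | either | yes, grade 3 | no | no |
| 0.8 / 0.8 | 2.5 / 3.5 | either | no: ALT above baseline | no: bilirubin > 2 | no: ALT not > 3 |
| 0.8 / 0.8 | 2.5 / 11 | either | no | no | no |
| 0.8 / 0.8 | 6 / 3.5 | absent | no | no | yes |
| 0.8 / 0.8 | 6 / 3.5 | present | no | no | no |
| 2.5 / 0.8 | 4.5 / 3.5 | either | no | no | no: 4.5 is below 2 x 2.5 = 5.0 and below 8.0 |
| 0.8 / 1.5 | 6 / 2.5 | either | no | no | no: 2.5 is below 2 x 1.5 = 3.0 |
| 2.5 / 0.8 | 6 / 3.5 | either | no | no | yes: 6 > 5.0 and > 3; 3.5 > 2 x 0.8 = 1.6 and ≥ 2 |

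Four results follow.

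1. **Intermediate transaminase rise.** Bilirubin above 2 x ULN with ALT/AST above baseline but not above 3 x ULN meets no row, with or without cholestasis, even at a bilirubin level that row 1 grades as 4.
2. **Cholestasis, normal baseline.** ALT/AST above 3 x ULN with bilirubin above 2 x ULN meets row 3 without cholestasis and no row with it.
3. **Elevated baseline.** A rise that misses one of the 2 x baseline conditions meets no row, as in the sixth and seventh lines.
4. **Contradiction on cholestasis.** In the last line Table 20 gives an action whether or not cholestasis is present. Section 8.3.3.1 gives the same patient that action only if cholestasis is absent.

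The other passages that might fill the gap were then read:

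- Section 8.3.3.1 starts at the same transaminase threshold above 3 x ULN, so it does not reach result 1. With cholestasis it states no treatment action. Its close-observation list applies to increases that require dose interruption, so it presupposes a decision taken elsewhere.
- The general rule in section 8.3.2 follows the organ system with the greatest toxicity. Bilirubin and transaminases belong to the same system, so it selects no row.
- The notes on confounding factors in Table 20 ask for obstruction and other causes to be excluded before interruption or reduction. They do not say what follows when such a cause is found.
- The reference in section 8.3.3 leads to the QTc rules.

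**The case against.** The strongest reply is that a fallback exists. Section 8.3.2.1 lists Tables 20 to 23 together as the procedure for toxicities suspected to be related to ribociclib, and Table 23 stands directly below the faulty reference in a section on all other adverse reactions. A careful reader would probably see that Table 23 is meant. Graded by bilirubin, its first steps resemble those of row 1: interruption at grades 2 and 3, discontinuation at grade 4. The differences lie mainly in recovery-time limits and recurrence. A reader might infer from the gap that these patients have no instruction at all; that is too strong. What remains is that the text names a different table and nowhere says that a liver pattern outside Table 20's rows counts as an other adverse reaction.

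A reader might also infer that every cholestatic case is uncovered. The documents do not support this: cholestatic bilirubin elevation without a transaminase rise is still in row 1, and the cholestasis condition in Table 20 stands only in the normal-baseline limb. Obstruction is also partly dealt with as an alternative cause to be excluded.

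The pattern of greatest concern, both values clearly raised with normal baseline and no cholestasis, has an explicit action in both Table 20 and section 8.3.3.1. That limits the severity.

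Finally, a reader might take the ALT rates of the cited phase III trial (15.6% any grade, 9.3% grade 3 or 4) as the size of the problem. They are not. Grade 3 or 4 ALT is above 5 x ULN, outside the intermediate pattern, and neither rate says how often bilirubin was raised too. The absence of bilirubin from that trial's list of grade 3 or 4 events in at least 5% of patients gives no bound either, because the gap begins at bilirubin grade 2.

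**Conclusion.** The point holds as a defect of wording in binding safety rules. Read as written, Table 20 gives no row to the intermediate combined rise, to the combined rise with cholestasis in patients with normal baseline, or to some combined rises from an elevated baseline. Table 20 and section 8.3.3.1 disagree on cholestasis for elevated baseline, and the fallback reference names the QTc table under a duplicated caption.

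This rests on taking the row headings as conditions, which is how they are worded. A site that treats them as loose labels could still pick a row, but different sites could pick different ones. The number of patients affected cannot be derived from the protocol, which gives no joint distribution of bilirubin, transaminases and cholestasis. The primary endpoint and the sample size are not touched. Severity: should-fix safety wording.

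**What to change.** - Reconcile the three row headings of Table 20 with each other and with section 8.3.3.1, including cholestasis and elevated baseline, so that each combined bilirubin and transaminase pattern has one stated route.
- Give Table 22 a caption that matches its QTc content.
- Correct the table reference in section 8.3.3, and state whether liver patterns outside Table 20's rows fall under that section.

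The action for each pattern is for the sponsor to set; none is proposed here. The cost is amendment wording in one table and the matching section, one caption and one cross-reference. No extra tests or visits and no change to the analysis are needed.

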13 TREATMENT DISCONTINUATION AND PREMATURE STUDY DISCONTINUATION

13.1 Protocol Treatment Discontinuation

13.1.1 Criteria for Discontinuing Protocol Treatment

Study drug discontinuation

Study drug interruption refers to a patient stopping either study drug during the course of the study, but then re-starting it at a later time in the study. If the study drug everolimus/ribociclib is interrupted for more than 4 weeks, the patient will be permanently discontinued from the study.

If the administration of study drug must be interrupted because of an unacceptable toxicity, dosing will be interrupted or modified according to rules described in TABLE 14, TABLE 15, TABLE 16, TABLE 17 for everolimus-cohort and TABLE 19, TABLE 20, TABLE 21, TABLE 22 and TABLE 23 for ribociclib-cohort. A patient who requires dose interruption (regardless of the reason for the interruption) lasting > 4 weeks (counting from the first day when a dose was missed) must discontinue study treatment. All study drug interruptions must be recorded on the appropriate Dosage Administration CRF.

Patients whose treatment is interrupted due to an adverse event or abnormal laboratory value must be followed at least once a week for 4 weeks and subsequently at 4 weeks intervals, until resolution or stabilization of the event, whichever comes first.

Study discontinuation refers to a patient's withdrawal from study drug. The reason for discontinuation from treatment must be recorded on the End of treatment CRF.

Patients who discontinue study drug > 4 weeks should be scheduled for an End of treatment Visit, as soon as possible, after discontinuing study drug, at which time all of the assessments listed for the End of treatment Visit will be performed. The complete End of treatment CRF documentation should be done within one week. The date and reason for stopping the study treatment should be recorded on the CRF.

Study drug will be discontinued for any of the following reasons:

- Tumor progression (as defined in section 10.2.)
- Toxicity/ Unacceptable adverse events
- Consent withdrawal/ Request by the patient
- Dose interruption of > 4 weeks
- Intercurrent illness that prevent further administration of study drug
- Need for any other types of anticancer therapy, except for palliative radiotherapy for bone lesions
- General or specific changes in the patient's condition which render the patient unacceptable for further treatment at the discretion of the investigator

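### Two ribociclib dose-modification rows are wrong as printed: Table 21 sets the anaemia bands at multiples of LLN, and Table 20 gives no restart dose after a first Grade 2 AST/ALT rise that recovers on days 22–28

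*Protocol*

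**What the plan says.** Section 8.3.2.1 introduces Tables 20 to 23 as the procedure for ribociclib toxicities and says that they also tell the site how to restart the drug after recovery.

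**Table 21, anaemia.** Grade 1 is printed as at least 10.0 times LLN, Grade 2 as 8.0 to below 10 times LLN, and Grade 3 as below 8.0 times LLN, all in g/dl. Grades 1 and 2 need no change. Grade 3 means interrupt until recovery to Grade 2 or better, then restart at the same dose.

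**Table 20, AST/ALT without bilirubin elevation, baseline grade 0 or 1 to Grade 2.** Ribociclib is interrupted. The restart condition is recovery to "baseline grade in ≤ 21 days or toxicity recurs, then reduce 1 dose level". The stop condition is "If toxicity recurs after two dose reductions or recovery to ≤ baseline grade is > 28 days, discontinue ribociclib".

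**Same cell, baseline grade 0 or 1 to Grade 3.** Interrupt "until resolved to ≤ baseline until resolved to ≤ baseline grade, then lower 1 dose level of ribociclib" and, for slow recovery, "If recovery to ≤ baseline grade > 28 days, discontinue ribociclib".

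**Table 20, total bilirubin Grade 2.** There are two restart branches: recovery to "grade 1 in ≤ 21 days, then maintain dose level", and recovery to "grade 1 in > 21 day or toxicity recurs, then reduce 1 dose level".

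**General limit.** Section 8.3.2.1 says "Patients who interrupt ribociclib therapy for more than 4 weeks must be discontinued from the study". Section 13.1.1 applies the same limit to "A patient who requires dose interruption (regardless of the reason for the interruption) lasting > 4 weeks".

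**The concern.** These are operative dosing rules, so each outcome that the protocol allows needs a stated action.

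The anaemia bands mark the point at which ribociclib is interrupted. A haemoglobin threshold of several times the lower limit of normal cannot be met, so the row misstates that point.

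The AST/ALT row is incomplete. A patient whose Grade 2 rise recovers on days 22–28 may restart, because only interruptions beyond 4 weeks end treatment, yet no dose is given. The choice has some weight: section 8.3.2 does not allow a reduced dose to be raised again, and Table 19 has only two steps below 600 mg (400 mg and 200 mg).

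**Working it through.** **1. Anaemia bands (Table 21).** The protocol gives no LLN for haemoglobin, so I assume 11.5 to 12.5 g/dL.

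| Assumed LLN (g/dL) | 8.0 × LLN | 10.0 × LLN |
|---|---|---|
| 11.5 | 92 | 115 |
| 12.0 | 96 | 120 |
| 12.5 | 100 | 125 |

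The result does not depend on the assumed LLN. Section 5.1 admits patients with haemoglobin of 9 g/dL. For such a patient to lie outside the printed Grade 3 band, LLN would have to be no more than 9 / 8.0 = 1.125 g/dL. Read literally, everyone is Grade 3 from day 1 and recovery to Grade 2 is impossible. With the factor removed, the printed numerals 10.0 and 8.0 are usable limits in g/dL.

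**2. Which AST/ALT sub-row applies.** Entry requires ALT and AST at or below 3.0 × ULN (section 5.1), and Table 20 starts Grade 2 above 3.0 × ULN. An eligible patient therefore enters at grade 0 or 1, and a first Grade 2 rise falls in the sub-row at issue.

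**3. Action by day of recovery, first event, as printed in Table 20.**

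| Row | By day 21 | Days 22–28 | Day 29 or later |
|---|---|---|---|
| AST/ALT, baseline 0–1 to Grade 2 | reduce one level | **none stated** | discontinue |
| AST/ALT, baseline 0–1 to Grade 3 | lower one level | lower one level | discontinue |
| AST/ALT, baseline 2 to Grade 3 | lower one level | lower one level | discontinue |
| Bilirubin Grade 2 | maintain | reduce one level | discontinue (general 4-week rule) |
| Bilirubin Grade 3 | lower one level | discontinue | discontinue |

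Listing every recovery day from 1 to 40 leaves exactly days 22 to 28 without an action in the first row. A recurrence is covered on every day, and no other interrupt-and-restart row has a gap.

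**4. Whether another section supplies the dose.**

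- Section 8.3.2 requires the site to consult the Study Office before continuing after a delay of more than two weeks, but names no dose.
- Sections 8.3.2.1 and 13.1.1 only cap the interruption at 4 weeks.
- Section 8.3.3.1 adds liver tests and work-up.
- Table 23 is for all other adverse reactions.
- The note on medical judgment stands under Table 21, not Table 20.

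None of these fills the gap.

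**The case against.** The strongest objection is that the AST/ALT gap may come from reading the PDF. The 21-day cut-off makes little sense without a second branch. The bilirubin Grade 2 row has two consecutive lines that begin almost alike, and the AST/ALT line looks like the start of one joined to the end of the other. The same cell has a doubled phrase ("until resolved to ≤ baseline until resolved to ≤ baseline grade, then lower 1 dose level of ribociclib") and prints 8.0 × ULN without the greater-than sign that section 8.3.3.1 gives. This stands: the text at hand cannot show whether a line was lost in the protocol or in the reading, so the source must be checked first. It does not explain the anaemia row well, because the same LLN factor appears in all three bands.

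The second objection is that the consequence is slight, and it also stands. Faster Grade 2 recovery, recurrence, and the more severe Grade 3 rise recovering by day 28 all lead to a one-level reduction, so a full-dose restart would run against all three. Every patient in the gap has also been off drug for more than two weeks and so must be discussed with the Study Office. A reader might infer that similar patients will in practice restart at different doses; the documents do not support that.

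Third, no clinician would apply the anaemia bands literally. Intensity is graded by CTCAE 4.03 (section 11.1 and Appendix IV), the actions in Table 21 follow the grade, and the note under it leaves room for judgment. That limits the harm, but the printed threshold is still wrong.

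**Conclusion.** Both rows need correcting, and the point is minor. The anaemia bands are wrong as written. The AST/ALT Grade 2 sub-row is incomplete as printed for a first event recovering on days 22–28, subject to the check of the source PDF. The day count assumes that recovery time and length of interruption run on the same clock.

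Two stronger readings should be resisted:

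- A reader might infer that the one-level reduction after recovery in 21 days or less is itself a mistake, because the bilirubin Grade 2 row maintains the dose there. Both AST/ALT Grade 3 sub-rows also reduce, so it may be deliberate, and only the sponsor can say.
- A reader might scale Table 11 to the 90 planned ribociclib patients. Grade 1–2 as worst grade is 52 − 25 − 6 = 21 of 334 for ALT and 50 − 16 − 3 = 31 of 334 for AST, if each patient is counted once at worst grade. These counts mix Grade 1 with Grade 2, leave out patients who pass through Grade 2 to Grade 3, give no recovery times, and come from patients without prior therapy for advanced disease who received letrozole only. They give neither the number affected nor a ceiling for it.

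No sample size, precision or primary-analysis figure changes.

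**What to change.** **Table 21, anaemia:** delete the LLN multiplier. State Grade 1 as 10.0 g/dL to below LLN, Grade 2 as 8.0 to below 10.0 g/dL, and Grade 3 as below 8.0 g/dL.

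**Table 20, AST/ALT from baseline 0–1 to Grade 2:** check the source PDF for a lost line. If it is absent there too, state that recovery on days 22–28, or recurrence, means reduce one dose level, and that recovery after more than 28 days means discontinue. Have the sponsor confirm whether recovery in 21 days or less means maintain or reduce, and keep the printed reduction until then.

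The cost is a wording change to two table rows in the next amendment and a notice to sites, with no extra procedures or patients.
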